5 STUDY TREATMENTS

5.1 Treatment Groups

All patients will be administered a 1000 mg APX001 loading dose BID on Study Day 1 (or over the first 24 hours if dosing starts in the evening) followed by a 600 mg APX001 maintenance dose QD on Study Day 2 and Study Day 3. From Study Day 4 onwards, the APX001 maintenance dose will be administered as either 600 mg APX001 IV infusion QD or may be switched to 800 mg PO QD when/if the criteria for oral dosing are met ([Section 5.5.3](#)).

5.2 Rationale for Dosing

In pharmacokinetic/pharmacodynamic (PK-PD) studies, immunocompromised mice were infected with one of three spp. of *Candida* (*C. albicans*, *C. glabrata*, or *C. auris*) and groups of animals were dosed with APX001 at different dose fractionations. The AUC/MIC ratio was determined to be the PK-PD variable that best correlated with antifungal efficacy as assessed by fungal burden (CFUs) in the kidney. The probability of target attainment (PTA) was calculated separately for each *Candida* spp. tested. The PTA calculation used the APX001A free drug AUC level at the stasis endpoint divided by the MIC required to inhibit the growth of 90% of organisms (MIC₉₀) of each of the *Candida* spp. tested.

The AUC level was estimated from a population PK model derived primarily from the Phase 1 PK data. The stasis endpoint was defined as the quantity of *Candida* spp. in CFUs just prior to APX001 administration compared to CFUs at the endpoint of assessment (i.e. 24 hours for *C. albicans*; 96 hours for *C. glabrata* and *C. auris*). The MIC data for the *Candida* strains tested were obtained from recent surveillance data.

Using the AUC at the stasis endpoint, along with the MIC₉₀ from the surveillance data and the predicted exposure at the dose regimen to be used in this study, the PTA for the 3 *Candida* spp. tested was shown to be approximately 100%. Further, sensitivity analyses were conducted to evaluate the PTA under different scenarios including increased variability of PK parameters and higher *Candida* spp. MIC₉₀ values. For both scenarios the PTA remained >90%.

In two Phase 1 studies in healthy volunteers, APX001 IV and PO formulations were safe and well tolerated. The majority of TEAEs were mild, transitory, and resolved without intervention. No DLTs were observed. Specifically, in the first-in-human Phase 1 clinical study, a loading dose regimen of APX001 1000 mg IV 2-hour infusion BID on Day 1, followed by a maintenance dose of APX001 600 mg IV 1-hour infusion QD on Days 2 through 7, was safe and well tolerated. In an additional Phase 1 study of APX001, a dose regimen consisting of a loading dose of APX001 1000 mg IV 3-hour infusion BID on Day 1, followed by a maintenance dose of APX001 600 mg IV 3-hour infusion QD on Days 2 through 7, and then APX001 800 mg orally QD on Days 8 through 42 was also safe and well tolerated.

Schedule

To ensure the safety and tolerability of APX001 dosing for 42 days, this study will use an APX001 dose and infusion duration already studied in Phase 1 for 42 days of therapy inclusive of IV and PO investigational drug therapy. The loading dose regimen of APX001 1000 mg IV BID over a 3-hour infusion followed by APX001 600 mg IV QD over a 3-hour infusion has been designed to optimize patient safety and tolerability during the study. At Study Day 4 and onward, provided the protocol-defined criteria for a PO switch are met, the patient may be switched to oral APX001 800 mg QD. Study drug will be administered for 14 days after clearance of *Candida* organisms from the bloodstream, and in accordance with clinical judgment as applicable for other infected sites, up to a maximum of 42 total days combined IV and PO APX001 therapy.

5.3 Randomization and Blinding

This is a non-randomized, open-label study.

5.4 Breaking the Blind

[figure not shown]
This is an open-label study.

5.5 Drug Supplies

5.5.1 Formulation and Packaging

APX001 Injection is formulated at a concentration of 20 mg/mL.

APX001 tablets are formulated at a strength of 200 mg white-coated tablets.

Although the size of the vial used for APX001 Injection and/or the APX001 tablet strength may be potentially modified (as re-supplies are manufactured), the APX001 doses to be administered will not change. Any changes will be detailed in the Pharmacy Manual.

All APX001 supplies will be labeled according to the requirements of local law and legislation, as well as current Good Manufacturing Practice and Good Clinical Practice (GCP) guidelines.

5.5.2 Study Drug Preparation and Dispensing

Study drug will be delivered to the study site by an authorized delegate of the Sponsor. Site staff who have been delegated the task of drug dispensing by the Investigator will dispense the appropriate treatment.

Additional details regarding study drug preparation and dispensing will be provided in the Pharmacy Manual.

5.5.3 Study Drug Administration

On Study Day 1 (or over the first 24 hours if started in the evening), a 1000 mg APX001 loading dose will be administered over 3 hours by IV infusion BID.

The infusion volume for both the 1000 mg and the 600 mg APX001 doses will be 250 mL.

On Study Day 4 and onward, an APX001 maintenance dose will be administered as either:

- 600 mg APX001 IV infusion QD over 3 hours, or
- 800 mg APX001 PO QD

Subjects who have completed a minimum of 3 days of IV APX001, are clinically stable as determined by the Investigator, and able to swallow tablets may switch from IV to PO dosing on Study Day 4 and onward. Study drug will be administered for a minimum of 14 days after clearance of *Candida* spp. Duration of APX001 treatment for other deep-seated sites of infection will be according to investigator judgment and treatment guidelines, but may not exceed up to a maximum of 6 weeks total (42 days, inclusive of the loading dose [Study Day 1]).

Tablets are to be administered at the same time each day, whole, and taken by mouth with water within 30 minutes of being removed from the refrigerator. No splitting or crushing of tablets is allowed.

5.5.4 Treatment Compliance

Study drug will be administered at the study site. Compliance with treatment dosing will be monitored and recorded by site personnel. If patients are discharged home with study treatment, compliance will be documented in a dosing diary.

5.5.5 Storage and Accountability

APX001 Injection will be stored at -20°C and tablets will be stored at 2 to 8°C in a secured location (locked) with access restricted to authorized personnel only. Detailed storage and handling instructions will be described in the study-specific Pharmacy Manual. Storage temperature will be monitored and recorded. Further details for storage and accountability of study drug will be provided in the Pharmacy Manual.

Upon receipt of study drug, the Investigator or designee will conduct a complete inventory of all study drug and ensure no damage occurred during shipment.

The Investigator will maintain adequate records documenting the receipt, use, loss, or other disposition of study drug. Drug accountability logs will identify the study drug code number and account for the disposition on a participant-by-participant basis, including specific dates and quantities. The drug accountability logs will be signed by the individual who dispenses the study drug and copies will be provided to the Sponsor.

All used and unused supplies will be appropriately inventoried and verified by the clinical research associate (CRA).

Any unused study drug will be returned to the Sponsor or destroyed on site per local standard operating procedure after monitoring has occurred.

5.6 Prior and Concomitant Medications and/or Procedures

5.6.1 Excluded Medications and/or Procedures

5.6.1.1 APX001A as a Victim Substrate for Cytochrome P450 Drug-drug Interactions

APX001A is metabolized by multiple CYP enzymes. Patients who are receiving or will receive strong inducers of multiple CYP enzymes (e.g., rifampin, carbamazepine, phenytoin, rifabutin) are excluded from participating in the study. Concomitant use of multiple medications that are strong inhibitors of different CYP pathways may increase levels of APX001A, which in consequence may potentially affect the safety risk of APX001 administration. Caution should be advised when co-administering medications that are strong inhibitors of CYP enzymes.

5.6.1.2 APX001A as a Perpetrator of Cytochrome P450 Drug-drug Interactions

APX001A was shown to be a weak inducer of CYP2B6; a moderate inducer of CYP1A2, CYP2C19, and CYP3A4; and a weak inhibitor of CYP2C9 and CYP2D6. The potential clinical significance of any APX001A DDI will depend on the extent of induction or inhibition and therapeutic margin of the specific victim substrate or substrates.

Co-administration of drugs that are metabolized by the CYP enzymes in this study should be approached with caution and the need for increased frequency of drug monitoring (where applicable) should be considered, especially for CYP substrates that have a narrow therapeutic window.

Refer to <http://medicine.iupui.edu/clinpharm/ddis/main-table/> for an exhaustive list of CYP enzyme inducers and inhibitors.

5.6.2 Prohibited Medications and/or Procedures

Once on study, patients may not receive concomitant systemic anti-fungal therapy for the treatment of candidemia and/or invasive candidiasis.

Subjects cannot have received any investigational drug within 30 days (or five half-lives whichever is longer) prior to dosing.

5.6.3 Documentation of Prior and Concomitant Medication Use

All prior medications received by the participant within 14 days prior to study drug administration and any concomitant medications used throughout the duration of the study will be recorded in the source documents and on the appropriate eCRF. The medication name, route of administration, dose, frequency, indication, and duration of treatment (start and stop dates) will be recorded.

6 STUDY PROCEDURES

6.1 Informed Consent

Written informed consent will be obtained from all participants prior to any study-specific procedures being performed. *C. auris* must be confirmed in culture prior to patient qualification for the study and dosing with study medication. Only those patients who have transient loss of capacity (e.g. mechanical ventilation, sedation) can have an LAR sign consent on their behalf. These patients will be allowed to make their own informed medical decisions and undergo the consent process if and when they are able to do so. Patients with permanent loss of capacity are not eligible for study participation.

6.2 Eligibility

The following cultures drawn or sampled as SOC, prior to informed consent, will determine study eligibility:

- Blood culture positive for *Candida* spp. confirmed to be *C. auris*
- Tissue, aspirate or fluid sampled from a normally sterile site, culture positive for *Candida* spp. confirmed to be *C. auris*

Limited antifungal treatment options are also a requirement for study eligibility. Limited treatment options may be due to one or more of the following factors:

- Resistance of *C. auris* to antifungal drug(s) in question
- Patient unable to tolerate antifungal treatment
- Antifungal contraindicated for given patient
- Inadequate response to antifungal treatment, including refractory and relapsing *C. auris* infection

Screening may start on confirmation of *Candida auris* candidemia or invasive candidiasis in a patient with limited antifungal treatment options.

6.3 Screening

Screening procedures must occur within a 120-hour window (for patients with candidemia) or 168-hour window (for patients with invasive candidiasis without candidemia) prior to qualification for the study.

The following procedures will be performed at Screening:

- Obtain informed consent
- Review inclusion/exclusion criteria
- Record medical history
- Record demography information
- Record vital signs, including temperature, blood pressure, heart rate, respiratory rate, oxygen saturation, and weight
- Intravascular catheter management and log of the line changes, to include any catheter tip culture results
- Perform clinical laboratory assessments (serum chemistry, hematology, coagulation, and urinalysis)
- Perform urine pregnancy test (for females of childbearing potential only)
- Collect blood cultures (daily)
- Collect other cultures and histopathology from other sites, as clinically indicated
- Perform imaging tests as clinically indicated to assess the site(s) and extent of invasive candidiasis infection at study baseline
- Record prior/concomitant medications
- Record adverse events

6.4 Treatment Period (up to 6 Weeks)

6.4.1 Baseline (Day -1 or Day 1, Pre-Dose)

Baseline procedures are to be completed predose and within 12 hours of the first dose of study drug (Day 1). The following procedures will be performed at Baseline (Day 1 Pre-dose):

- Confirm inclusion/exclusion criteria
- Perform APACHE II score calculation ([Appendix C](#))
- Collect blood culture for *Candida* spp.
- Collect other cultures and histopathology from other sites, as clinically indicated

- Perform imaging investigations as clinically indicated to define the site(s) and extent of invasive candidiasis infection
- Intravascular catheter management and log of the line changes; any indwelling intravascular catheters should be removed and catheter tips cultured within 24 hours of starting APX001 dosing; entrance site tissue should also be cultured if it appears infected
- Implementation of other fungal infection control measures, as clinically indicated
- Record vital signs, including temperature, blood pressure, heart rate, respiratory rate, oxygen saturation, and weight; height will be collected (from the patient's medical record) at Baseline only
- Perform clinical laboratory assessments (serum chemistry, hematology, coagulation and urinalysis)
- Perform 12-lead ECG
- Perform urine pregnancy test (for females of childbearing potential only)
- Perform complete physical examination including an assessment of general appearance, skin, eyes, heart, chest, abdomen, and the body site that corresponds to the entry site of candidemia (e.g., central venous catheter entry site) and/or the site of invasive candidiasis, if applicable, and a neurological examination (cranial nerve, sensory and motor examination, reflex and gait testing, coordination assessment)
- Perform dilated fundoscopic examination. This exam should be performed at least once during the baseline period, which exclusively for this assessment may be up to Day 3 of the study.
- Collect plasma sample for PK (APX001 [prodrug] and APX001A [active moiety]). Plasma samples for PK will be collected at the same time as samples are collected for the study's clinical laboratory assessments.
- Collect serum sample for analysis of(1,3)- β -D-glucan
- Record concomitant medications
- Record adverse events

6.4.2 Study Drug Treatment (\leq 6 Weeks)

Day 1 dose

Prior to the initiation of the first APX001 dose, a diagnosis of candidemia and/or invasive candidiasis caused by *C. auris* (in a single or mixed *Candida* spp. infection) must be confirmed within 120 hours (for candidemia) or 168 hours (for invasive candidiasis without candidemia) of formal qualification for the study. The initiation of the first dose of APX001 must occur within 12 hours of qualification for the study.

- Study drug to be administered as a 3-hour IV loading dose BID on Day 1 (or over the first 24 hours if started in the evening).

Day 2 onwards (maximum to Day 42)

- On Study Days 2 to 3, study drug to be administered over 3 hours by IV QD; on Day 4 and onward, oral administration of the study drug may be considered if the patient meets the IV to oral switch criteria
- Study drug to be administered for a minimum of 14 days after clearance of *Candida* organisms from the bloodstream or other infected sites,
- Maximum duration of study drug treatment is up to 6 weeks total (42 days, inclusive of the loading dose [Study Day 1])

The following procedures will be performed during the period of Study Drug Treatment:

- For patients with candidemia (with or without invasive candidiasis) **daily** blood cultures are to be performed on Days 1 through 4 (minimum), continuing until 2 negative blood culture results are reported from 2 consecutive samples. (Considered negative at least 48 hours after collection).
- For patients with invasive candidiasis, with or without candidemia, appropriate material from the infected site(s) is to be sampled for culture or histopathology to monitor the progress of infection, as clinically indicated until mycological and/or clinical resolution.
- Imaging tests are to be performed as clinically indicated to monitor the site(s), extent and progress of invasive candidiasis infection
- Intravascular catheter management log; all changes are to be recorded until EOST while inpatient, and as clinically indicated thereafter or for outpatients
- Daily vital signs, including temperature, blood pressure, heart rate, respiratory rate, oxygen saturation, and weight while an inpatient. Measurements are to be continued twice weekly while on treatment as an outpatient.

During Study Drug Treatment, twice weekly visits are required with a minimum window of 2 days and a maximum window of 4 days. Subjects who are outpatients will be asked to record daily dosing on a diary and bring the diary and study drug bottles with them to every clinic visit.

- Perform clinical laboratory assessments (serum chemistry, hematology, coagulation and urinalysis) twice weekly
- Perform urine pregnancy test (for females of childbearing potential only); every 30 days if required by local regulations
- Perform neurological examinations twice weekly
- Perform focused, symptom-based physical examination, as clinically indicated, once weekly

- Collect plasma sample for PK (APX001 [prodrug] and APX001A [active moiety]) twice weekly. Plasma samples for PK will be collected at the same time as samples are collected for the study's clinical laboratory assessments.
 - Optional: If body fluids are sampled as part of routine patient management (e.g., bronchoalveolar lavage, lumbar puncture, paracentesis, vitreous fluid collection, abscess drainage, etc.), within approximately 2 hours of blood sampling for PK, these samples may be stored for future analysis of APX001 levels
- Record concomitant medications
- Assess adverse events

6.4.3 End of Study Drug Treatment (≤6 Weeks)

The EOST for patients completing the study is at least 14 days from the date of clearance of candidemia, as documented by the first of the two consecutive negative blood cultures up to a maximum of 6 weeks total (42 days, inclusive of the loading dose [Study Day 1]). For patients with a deep-seated site of infection amenable to sampling, EOST is after at least one negative tissue culture or aspirate/fluid, up to a maximum of 6 weeks total (42 days, inclusive of the loading dose [Study Day 1]).

- For patients with a deep-seated site of infection involving visceral organs from which a tissue culture is not obtainable, EOST is after the resolution of the attributable clinical signs of infection recorded at Baseline, and, as applicable, radiological improvement associated with the site of infection, up to a maximum of 6 weeks total.

The following procedures will be performed at EOST:

- Collect blood cultures for *Candida* spp.
- Collect other cultures and histopathology from other sites, as clinically indicated
- Perform imaging tests as clinically indicated to monitor the site(s) and extent of invasive candidiasis infection
- Perform dilated fundoscopic examination (only required in those patients who had baseline positive fundoscopic findings [up to Day 3], or as clinically indicated)
- Intravascular catheter management log
- Record vital signs, including temperature, blood pressure, heart rate, respiratory rate, oxygen saturation, and weight
- Perform clinical laboratory assessments (serum chemistry, hematology, coagulation and urinalysis)
- Perform 12-lead ECG
- Perform urine pregnancy test (for females of childbearing potential only)
- Perform neurological examination

- Perform focused, symptom-based physical examination as clinically indicated
- Collect plasma sample for PK (APX001 [prodrug] and APX001A [active moiety]). Plasma samples for PK will be collected at the same time as samples are collected for the study's clinical laboratory assessments.
- Collect serum sample for analysis of(1,3)- β -D-glucan
- Evaluate treatment outcome
- Record concomitant medications
- Assess adverse events

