On Study Day 1 (or over the first 24 hours if dosing starts in the evening), a 1000 mg APX001 loading dose will be administered over 3 hours by IV infusion twice daily (BID). On Study Days 2 and 3, a 600 mg APX001 maintenance dose will be administered over 3 hours by IV infusion once daily (QD). On Study Day 4 and onward, the APX001 maintenance dose will be administered as either 600 mg APX001 IV infusion QD over 3 hours or 800 mg PO QD. Patients who have completed a minimum of 3 days of IV APX001, are clinically stable as determined by the Investigator, and are able to swallow tablets, may switch from IV to PO dosing on Study Day 4 and onward. Study drug will be administered for 14 days after clearance of *Candida* organisms from the bloodstream, and in accordance with clinical judgment as applicable for other infected sites, up to a maximum of 42 days.

Patients will be monitored by daily blood culture from signing informed consent, through dosing, during Study Drug Treatment until 2 consecutive blood cultures are negative for *Candida* spp., at EOST, and at 2 and 4 weeks after EOST, or Early Termination. For patients diagnosed with invasive candidiasis, relevant cultures, histopathology, and imaging tests to assess the site(s), extent, progress, and outcome of the *Candida* infection will be conducted as clinically indicated. All results should be recorded in the electronic Case Report Form. The management of intravascular catheters, intravascular devices, and, if applicable, any drains will be recorded, including any associated microbiology results.

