***APX001 IV or PO QD Maintenance Dosing**

For patients with invasive candidiasis, maintenance dosing will continue until at least one negative tissue culture or aspirate/fluid

For patients with a deep-seated site of infection from which a tissue culture is not obtainable, maintenance dosing should continue until after the resolution of the attributable clinical signs of infection recorded at Baseline, and, as applicable, radiological improvement associated with the site of infection maximum 6 weeks (42 days)

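### For deep-seated infection the protocol gives inconsistent rules for the earliest end of treatment, so the earliest permitted EOST, the primary time point, can differ by up to 14 days

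*Protocol*

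**What the plan says.** For a deep-seated site, the documents describe the end of treatment in three ways.

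- **After a negative site culture.** Protocol 6.4.3: "For patients with a deep-seated site of infection amenable to sampling, EOST is after at least one negative tissue culture or aspirate/fluid". The same section states a 14-day floor for candidemia but none for deep sites. The text under Figure 1, repeated in SAP 2.2, agrees: "For patients with invasive candidiasis, maintenance dosing will continue until at least one negative tissue culture or aspirate/fluid". Where no culture can be obtained, resolution of the baseline signs takes its place (with radiological improvement if applicable), again with no minimum.
- **Fourteen days after clearance.** Protocol 6.4.2: "Study drug to be administered for a minimum of 14 days after clearance of *Candida* organisms from the bloodstream or other infected sites".
- **By judgment.** Protocol 5.5.3: "Duration of APX001 treatment for other deep-seated sites of infection will be according to investigator judgment and treatment guidelines". Protocol 3.1 has treatment "in accordance with clinical judgment as applicable for other infected sites", and Protocol 5.2 and SAP 2.2 say the same in substance.

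The 42-day cap applies throughout. Footnote c of the schedule of procedures (Protocol Appendix A) places EOST after dosing is complete. EOST is the time point of the primary endpoint (Protocol 7.1, SAP 6.1) and the origin of the 2- and 4-week follow-up. Besides its culture criterion, Treatment Success (Protocol 7.4.1, SAP 6.4.1) requires the patient to be alive at EOST and to have had no other systemic antifungal up to then. The SAP does not define EOST further.

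**The concern.** EOST is set by the rule for stopping drug, so an inconsistent stopping rule makes the primary time point inconsistent. Two centres could treat similar patients, each follow a section of the protocol, and have the primary endpoint judged up to two weeks apart in the course of disease.

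Two of the success criteria accumulate over time: survival, and freedom from other systemic antifungals. A later EOST gives more time in which to fail. The follow-up visits move with EOST as well.

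The Per-Protocol Population is also affected. It requires 80% of intended doses (Protocol 9.1, SAP 7.2.4), and the number intended depends on which section sets the course length.

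**Working it through.** The documents derive no figure on this point, so there is none to reproduce. The check is date arithmetic on the protocol's own rules.

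**Inputs.** Let s be the study day of the first negative site culture, taken as site clearance (an assumption, since the protocol dates clearance only for blood). Let b be the day of blood clearance, the first of two consecutive negative cultures (Protocol 6.4.3). The cap is Day 42. Day 1 carries two doses and each later day one (Protocol 5.1), so doses through Day d number d + 1.

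**Site-only infection.**

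- Earliest EOST under 6.4.3: s
- Earliest EOST under 6.4.2: min(s + 14, 42)
- Gap: min(14, 42 − s)
- Dose share if 6.4.2 sets the intended course but the patient stops at s: (s + 1) / (min(s + 14, 42) + 1)

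| s | 6.4.3 | 6.4.2 | Gap (days) | Dose share |
|---|---|---|---|---|
| 10 | 10 | 24 | 14 | 11/25 = 44% |
| 20 | 20 | 34 | 14 | 21/35 = 60% |
| 28 | 28 | 42 | 14 | 29/43 = 67.4% |
| 30 | 30 | 42 | 12 | 31/43 = 72.1% |
| 34 | 34 | 42 | 8 | 35/43 = 81.4% |
| 42 | 42 | 42 | 0 | 100% |

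The gap is 14 days for any clearance up to Day 28 and then shrinks to zero at the cap. For s = 10, the 4-week visit falls on 10 + 28 = Day 38 or 24 + 28 = Day 52. The 80% threshold is first reached at s = 34 (Day 33 gives 34/43 = 79.1%).

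**Site infection with candidemia.** The later of the site and blood rules governs:

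- 6.4.3: max(s, min(b + 14, 42))
- 6.4.2: max(min(s + 14, 42), min(b + 14, 42))

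| b | s | 6.4.3 | 6.4.2 | Gap (days) |
|---|---|---|---|---|
| 4 | 4 | 18 | 18 | 0 |
| 4 | 10 | 18 | 24 | 6 |
| 4 | 20 | 20 | 34 | 14 |
| 10 | 10 | 24 | 24 | 0 |

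**Effect on classification.** Take a site-only patient with s = 10 who dies on Day 17. If treatment ended on Day 10 under 6.4.3, the patient was alive at EOST and can be a primary success, with the death counted in follow-up. If treatment was to run to Day 24 under 6.4.2, the patient is a primary failure. A new systemic antifungal on Day 17 works the same way, provided that seven days after EOST is not read as immediately following it, which the note to the success definition would count against success.

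**Time at risk, on an assumption.** The documents give no mortality rate. If 30-day mortality were m with constant hazard, the risk of death over 14 days would be 1 − (1 − m)^(14/30): 9.9% for m = 20%, 15.3% for 30%, 21.2% for 40% and 27.6% for 50%. Patients whose site has cleared may be at lower risk, so this only shows that the interval is not negligible.

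**The case against.** **The rules are lower bounds.** A reader might infer that they cannot all be followed for one patient. The documents do not support that: a patient cleared on Day 10 and treated through Day 24 satisfies 6.4.2, 6.4.3, the Figure 1 text and the judgment clauses together. What remains is that the earliest permitted stop differs, and that stopping just after the negative culture complies with one section and breaches another.

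**Regrowth.** A reader might infer that regrowth on Day 17 is a primary failure under 6.4.2 and a relapse under 6.4.3. That does not follow. Under 6.4.2 the patient is still on drug on Day 17 and may clear again before Day 42, and the site criterion asks for only one negative culture. Site sampling may also stop after that culture (Protocol 7.5.2), so regrowth could go unseen. Death and new antifungal use do not depend on that argument.

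**The candidemia wording.** Some sections say 14 days and others a minimum of 14 days. Exactly 14 days meets both, and this is not a deep-site issue.

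**The 14-day floor for sites rests on one bullet.** The bullet in 6.4.2 ends in a comma and may be incomplete, while several other sections leave sites to judgment. That may explain how the inconsistency arose, but a centre reading 6.4.2 still sees a requirement.

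**Existing safeguards.** One Data Review Committee adjudicates every patient. SAP 7.4.2 reports sustained success, relapse and reasons at both follow-up visits. Day 30 survival counts from first dose and does not move with EOST. SAP 7.3.7 already summarizes days of exposure, which is close to the study day of EOST. These help, but adjudication does not settle which EOST date applies, and the exposure summary is overall only, not by infection type.

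**Reporting delay.** Protocol 6.4.2 counts a blood culture as negative only after at least 48 hours. If the same held for site cultures, a Day 10 sample could not end treatment before Day 12, and the practical gap in that example would be 24 − 12 = 12 days.

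**Conclusion.** The inconsistency is real and should be resolved. For a deep-seated site that can be sampled, the earliest permitted EOST differs by 14 days when infection is site-only and clears by Day 28. The gap is smaller after Day 28, and partly or wholly absorbed when the candidemia rule governs. These figures take the first negative site culture as clearance and count from the sampling date.

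Within the gap, a death or a new systemic antifungal changes the primary classification. Per-Protocol membership is also ambiguous: in the Day 10 example the patient has 44% of intended doses under 6.4.2 and 100% under 6.4.3. The oral compliance formula in SAP 7.3.7 does not settle this, because it covers oral dosing only, ends its denominator at the last oral dose, and is not tied to the Per-Protocol criterion.

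The effect on the overall success rate cannot be computed. The number of deep-seated cases among the approximately 15 patients is not stated, and exclusion criterion 13 removes several types. A reader might take 1/15 = 6.7 percentage points as the effect, but that is only the weight of one patient. It says nothing about how many would be reclassified.

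**What to change.** 1. Reconcile Protocol 3.1, Figure 1, 5.2, 5.5.3, 6.4.2 and 6.4.3 and SAP 2.2 so that one end-of-treatment rule per infection type appears in all of them. Which rule applies is for the sponsor's clinical team.
2. Use that rule in SAP 7.2.4 to define intended doses for the 80% criterion.
3. Split the exposure-day summary already planned in SAP 7.3.7 by infection type (candidemia, deep-seated, both) and show it beside the primary result, so that readers can see when EOST fell.

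The cost is a protocol clarification, which goes through the usual amendment review, one sentence in the SAP, and a subdivision of a planned table. No new data are needed.
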